9.6 DATA MANAGEMENT

The survey will be conducted according to the Standard Operating Procedures (SOPs) of IQVIA/ IQVIA Medical Radar. The datasets extracted from the databases will be stored at IQVIA files to allow analysis in the future.

Collected data will be entered and stored in a database specific to the survey and the country. A study database will be created by merging of databases of each country.

Data will be checked in terms of consistency before data analysis:

- removal of duplicates (if required),
- data labelling and data formatting,
- range and consistency checks for each variable to identify potential non admissible values,
- cross-check the consistency of data for related variables (if feasible).

9.6.1 **Data collection**

The data collection period will last about 4 to 8 weeks during the fieldwork period (expected in February and March) every year, starting in 2019 and taking place annually until 2022. It will be conducted in parallel in the five countries.

The survey will be conducted by IQVIA Medical Radar, a division of IQVIA specialized in the conduct of phone and web surveys for more than 20 years. IQVIA Medical Radar will create a web-based instance survey. The lists of physicians will be loaded into separate databases for the management of the survey.

Physicians will be randomly contacted, mainly by email and also by phone when needed, according to their stratum by the IQVIA Medical Radar team. Their recruitment will be done as follows:

Physicians will be invited to participate in the survey (via phone calls or emails).
 The survey background and objectives, the contact information for questions, and the proposed compensation will be explained to the physicians at this step. If they

agree to participate in the survey, they will receive a link to access the survey and the instructions for the web-questionnaire completion.

- If the questionnaire is not completed and sent to IQVIA Medical Radar, the physicians will be sent a reminder by email one week after the start of the survey.
- If the target is not achieved in the stratum, a reminder by phone will be conducted 1.5 weeks after the start of the survey.
- If the questionnaire is still not completed and sent to IQVIA Medical Radar, the physicians will be sent a last reminder by email two weeks after the start of the survey.

If necessary, the recruitment will be performed by phone to achieve the target.

A physician will be considered as contacted if he/she has:

- completed the survey and sent it back to IQVIA Medical Radar,
- been reached out by phone or have opened their email (if the score is technically available in their country)
- refused to participate

Moreover, a physician will be considered as unreachable if he/she has been contacted at least 3 times without any answer.

For each physician of the sample file, the number of contacts, and the date and time when he/she completed the web questionnaire will be recorded. The recruitments in each country will be stopped when the target is reached.

9.6.2 Approaches for increasing the response rate

Physicians are increasingly contacted to participate in web or phone surveys. Their overall response rate of participation remains low according to international studies (13-15). Holbrook et al. showed that the response rate to surveys continues to decline over time, but a lower rate does not appear to reduce the representativeness of a demographic survey (15). VanGeest et al. conducted a systematic review of 66 published reports on efforts to perform for improving response rates (16). Two general strategies were explored: incentives-based approaches and survey design-based approaches. Financial incentives, even little ones, were effective in improving physician response rates while non-monetary incentives were much less effective. These measures include the use of a short questionnaire, and questionnaires personalized, and approved by professional associations.

In order to increase the response rate, three actions will be applied to this survey:

- A compensation fee will be proposed to physicians for their participation in the survey.
- All physicians will be sent an email or contacted by experienced operators of IQVIA Medical Radar with extensive experience in conducting health related surveys.

• Each physician will be emailed or called up to 3-5 times before being considered as "not reachable", and reminders will be sent by email if IQVIA Medical Radar does not receive the web questionnaire.

9.7 DATA ANALYSIS

9.7.1 General statistical consideration

The statistical analysis will be conducted using the SAS® software (like SAS 9.3) on WindowsTM (SAS Institute, North Carolina, USA).

A detailed statistical analysis plan (SAP), that could support independent replication of the study results, will be agreed on prior to the start of the analysis. Table shells, exact definitions of all variables (e.g. details on the calculation of average daily dose), the categories of variables to appear in the tables (e.g. age), and subgroup analyses of patients will be defined in the SAP.

The statistical results of the five countries will be presented annually in the same report. Results will be presented by country. Due to the low sample size no stratification by specialty is planned.

All the analysis will be descriptive in nature and no statistical comparison will be done in this study.

The survey will be performed once per year for four years. Physicians will always be asked annually to provide information on the last patient they saw who they had prescribed Intuniv[®] to: for the first report patients for who they had prescribed Intuniv[®] since launch; for later reports the most recent patients who they had seen for who they had prescribed Intuniv[®] to within the previous 12 months period (patients' selection window), regardless whether the patient had received an Intuniv[®] prescription at his/ her last visit. The observation period for the first report will be the country-specific launch date to 31 March 2019; for consecutive reports – until 31 March of the respective study year. The last survey will cover the period until 31 March 2022.

9.7.2 Representativeness of participating physicians- Analysis of non-participation or refusal to participate rate

As often required by the Authorities, the following different cases of total non-response will be distinguished and analyzed:

- Targeted physicians: Physicians reached to whom an email or mail has been sent, or have been called.
- Contacted physicians: Physicians who have been reached out by phone or have opened their email (if the score is technically available in their country).
- Physicians who agreed to participate: Physicians willing to participate in the survey (e.g. by phone or by clicking on the link provided in the recruitment email).
- Physicians with complete questionnaire: Physicians who actually completed the questionnaire until its end.

The physicians' participation in the survey will be examined via different ratios:

- Contact rate = contacted physicians / targeted physicians
- Response rate = Physicians who agreed to participate/ contacted physicians
- Cooperation rate = Physicians with complete questionnaire / Physicians who agreed to participate
- Refusal rate = contacted physicians minus physicians who agreed to participate / Physicians contacted

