9.2 SETTING

The survey will be conducted among prescribers of Intuniv[®] in the selected countries (Belgium, Finland, Ireland, and Netherlands) and conducted annually from 2019 to 2022. In order to minimize selection bias, physicians will be randomly recruited using nationally representative external lists (OneKey lists). The prescriber sample selected will be described by specialty, graduation year, gender, and type of location (e.g. urban/rural). It is planned to collect data for 50 to 100 patients per country who have been prescribed Intuniv[®] at least once during the study period. Recruitment will occur from the total population of healthcare practitioner groups who are most likely to treat patients with ADHD. Physicians will be recruited as described in 9.5.1. The physicians who are eligible for participation will be instructed to select the patient record based on the last patient they have seen, for who at any time in the last 12 months (or, for the first report, since country specific launch) they have prescribed Intuniv[®] (whether or not Intuniv[®] was prescribed at that last visit). Recruitment of physicians will be done at random for each annual survey, with the aim to avoid having the same physicians in each survey. However, overlaps within the groups of physicians are still possible. The number of physicians per specialty who provided data for the survey will be included in the report. Information regarding the total population of physicians will also be included. One to 10 patients per physician may be reported, with the most recent patients being reported first.

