9.2.1 Inclusion criteria

The survey will be conducted among physicians meeting the following inclusion criteria:

• Prescribers of Intuniv[®], i.e. physicians who know and have prescribed the drug at least once during the previous 12 months (or, for the first report, since country specific launch) (paediatricians, psychiatrists, neurologists and GPs)

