9.5 STUDY SIZE

9.5.1 **Sampling plan**

Per country and year, the target is to collect data from 50 to 100 patients, who have been prescribed Intuniv[®] at least once during the study period, provided by representative physicians qualified to treat patients with ADHD. It is planned to annually recruit 15 to 20 prescribers of Intuniv[®] per country who will be requested to complete, if possible, 1 to 10 medical record extracts.

A random sampling plan will be developed. Prescribers will be sampled among the lists of paediatricians, GPs, neurologists and psychiatrists.

Due to the low prescribing base, no quotas by physician types will be set. As many patient medical records (anticipated maximum: 100 records per country) from as many prescribing physicians who are willing to participate will be collected.

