9.9 LIMITATIONS OF THE RESEARCH METHODS

9.9.1 Possible selection bias due to voluntary participation

The selection bias of physicians participating in a survey is an inherent bias to any study based on volunteer participation. In order to quantify any selection bias, the distribution of each stratification criterion of healthcare professional (country and specialty) will be compared between participants and non-participants.

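### The participation rates (9.7.2) and the selection-bias comparison (9.9.1) take no account of eligibility, so non-prescribing is mixed with non-response

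*Protocol*

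**What the plan says.** **Who may take part.** Protocol section 9.2.1 limits the survey to "physicians who know and have prescribed the drug at least once during the previous 12 months" (for the first report, since country launch).

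**Who is approached.** Section 9.2 states: "Recruitment will occur from the total population of healthcare practitioner groups who are most likely to treat patients with ADHD". Section 9.5.1 adds: "Prescribers will be sampled among the lists of paediatricians, GPs, neurologists and psychiatrists". It also says: "Due to the low prescribing base, no quotas by physician types will be set". List cleaning under section 9.2.2 removes inactive and retired physicians. The exclusions checked at the start of the questionnaire are not treating patients and conflict of interest. Prescriber status appears in neither step.

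**How participation is measured.** Section 9.7.2 has four statuses: targeted, contacted (reached by phone or opened the email), agreed (for example by phone or by clicking the link) and complete. Apart from the contact rate, three ratios are built on them:
- The first takes everyone contacted as its base: "Response rate = Physicians who agreed to participate/ contacted physicians".
- The next keeps that base and counts all who did not agree: "Refusal rate = contacted physicians minus physicians who agreed to participate / Physicians contacted".
- The last starts from those who agreed, whether or not they turn out to be eligible: "Cooperation rate = Physicians with complete questionnaire / Physicians who agreed to participate".

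**How selection bias is to be quantified.** Section 9.9.1 says that the distribution of country and specialty "will be compared between participants and non-participants". It does not restrict the non-participants to eligible physicians.

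**The concern.** The population of interest is prescribers, but the denominators are contacted physicians of any kind. No status separates a physician who could not take part from one who chose not to, and none covers physicians whose eligibility never became known.

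The reports claim a representative sample, and only 15 to 20 prescribers per country per year are planned (section 9.5.1). A reader of the annual report sent to EMA will want to know whether those few resemble prescribers at large. Rates and comparisons that move with the rarity of prescribing do not answer that. A very low response rate could simply mean that few physicians on the lists prescribe the drug. A marked specialty imbalance could mean only that some specialties prescribe it more than others.

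**Working it through.** **Inputs.** The definitions are those of section 9.7.2, reading the refusal formula with its numerator in brackets. The protocol gives no expected response, refusal or cooperation rate and no prescriber share, so there is no planned figure to reproduce. Every number fed in below is an assumption.

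Let π be the prescriber share of contacted physicians, a the agreement among prescribers, c the agreement or click-through among non-prescribers, and k the completion among agreeing prescribers. Assume that non-prescribers who click through are screened out.

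**Formulas as written**
- Response = πa + (1 − π)c
- Refusal = 1 − response
- Cooperation = πak / [πa + (1 − π)c]

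Among eligible physicians the same quantities are a, 1 − a and k.

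**Illustration 1: 400 contacted, a = 50%, c = 5%, k = 90%**

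| | π = 10% | π = 20% | Eligible only |
|---|---|---|---|
| Prescribers / non-prescribers | 40 / 360 | 80 / 320 | |
| Agreed | 20 + 18 = 38 | 40 + 16 = 56 | |
| Response | 38/400 = 9.5% | 56/400 = 14% | 50% |
| Refusal | 90.5% | 86% | 50% |
| Complete | 18 | 36 | |
| Cooperation | 18/38 = 47% | 36/56 = 64% | 90% |

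**Illustration 2: a = 30%, k = 90%, with π and c varied.** Eligible-only values are response 30%, refusal 70% and cooperation 90%.

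| π | Response, c = 0 | Non-prescribers among counted refusers, c = 0 | Response, c = 10% | Cooperation, c = 10% |
|---|---|---|---|---|
| 5% | 1.5% | 96% | 11% | 12% |
| 10% | 3% | 93% | 12% | 22% |
| 20% | 6% | 85% | 14% | 39% |
| 50% | 15% | 59% | 20% | 68% |

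With c = 0, cooperation stays at 90% and only response and refusal are distorted. With c = 30%, equal to a, response happens to be right at 30% but cooperation falls to πk, which is 9% at π = 10%. Both rates are right together only when every contacted physician is a prescriber, or when c = 0 and a = 0, which is of no interest.

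**Illustration 3: the specialty comparison in 9.9.1.** Assume a list of 1,000 physicians and the same 30% participation among prescribers in every specialty, so that there is no differential refusal.

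| Specialty | On list | Prescriber share | Prescribers | Participants |
|---|---|---|---|---|
| GPs | 700 | 2% | 14 | 4.2 |
| Psychiatrists | 150 | 30% | 45 | 13.5 |
| Paediatricians | 100 | 30% | 30 | 9.0 |
| Neurologists | 50 | 10% | 5 | 1.5 |
| Total | 1,000 | | 94 | 28.2 |

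- GPs among participants: 4.2/28.2 = 14.9%.
- GPs among all non-participants: (700 − 4.2)/(1,000 − 28.2) = 695.8/971.8 = 71.6%.
- GPs among eligible non-participants: (14 − 4.2)/(94 − 28.2) = 9.8/65.8 = 14.9%.

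The comparison without an eligibility restriction shows a large imbalance where none exists. It can also err the other way. If prescribers in the high-prescribing specialties were the ones who declined more often, the participants' mix would move towards that of the whole list, and real differential refusal would narrow the visible gap.

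**The case against.** Several points on the other side are sound.

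- **Other checks exist.** A reader might infer that these ratios are the study's only guard against selection bias. Section 9.2 also describes the sample by specialty, graduation year, gender and location, and promises counts per specialty and information on the total physician population. Section 9.8.1 reports the percentage of physicians without a complete analysable questionnaire, and section 9.9.2 concedes limited generalisability. These do not cure the ratios, because the total physician population is again not the prescriber population.
- **Not every non-prescriber becomes a refuser.** Those who click or agree by phone are counted as agreed, which raises the response rate.
- **The cooperation effect is conditional.** The protocol does not say when prescriber status is established, and the questionnaire, a stand-alone document, is not shown. It may already ask about prescribing, and it governs how a screened-out physician is coded. That this rate is lowered is an inference.
- **The magnitudes are illustrative.** Section 9.5.1 indicates that prescribers are few but gives no share.
- **The consequences are bounded.** The rates are descriptive, weight no estimate and trigger no decision. A reader might infer that the utilisation results or the knowledge criterion (80% of physicians answering 75% of questions correctly) are miscalculated. They do not use these rates.

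What remains is that 9.7.2 writes out the statuses and ratios in full, so this is not detail left to the SAP. Section 9.6.1 even lists having refused as a contact outcome of its own, yet the refusal rate ignores it and counts an opened, unanswered email in the same way.

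**Conclusion.** The concern holds as a fault in stated definitions. Followed as written, 9.7.2 counts contacted non-prescribers who do not proceed as refusers. Section 9.9.1 compares participating prescribers with a group that includes non-prescribers. That much follows from the text alone, given that some contacted physicians do not prescribe Intuniv. The effect on cooperation also requires that some non-prescribers click through and are then screened out.

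The size cannot be established from the protocol. Under the assumptions of illustration 1 the response rate is understated by a factor of about five at a 10% prescriber share (9.5% against 50%) and between three and four at 20% (14% against 50%). Other inputs give other values, and enough click-through can make the response rate look right while cooperation collapses. The harm is confined to the interpretation of representativeness. The change should be made before the first fieldwork, because eligibility status is hard to recover afterwards.

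**What to change.** 1. Record prescriber status within the window at first phone or email contact, or on the first questionnaire page.
2. In 9.7.2 add two statuses: ineligible (non-prescriber or excluded at screening) and eligibility unknown.
3. Report response and cooperation among known-eligible physicians. For response, give a range: eligible physicians who agreed divided by known-eligible physicians (all unknowns ineligible), down to the same numerator divided by known-eligible plus unknown (all unknowns eligible). A stated estimate of the eligible share among unknowns may be used instead.
4. Count explicit refusals separately from no reply, rather than as the complement of response.
5. In 9.9.1 compare participants with known-eligible non-participants by specialty, and report screened-out non-prescribers separately by specialty.

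**Cost.** One screening question (if the questionnaire does not already contain it), two status codes and redefined denominators, with no extra physicians to recruit. Two limits remain. Physicians who open an email and never answer have unknown eligibility, so the range may be wide or rest on an assumption. With 15 to 20 prescribers per country per year, specialty cells will be sparse, so the comparison should be shown as counts and read cautiously.

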9.7.3 Questionnaire analysis

The reports will include descriptive statistics of all parameters analyzed. As part of this analysis, the description of missing data for each outcome of interest will be provided. Missing values are expected to be few and distributed at random. Since there is no applicable method unanimously accepted, there will be no replacement or imputation of missing data (17).

For continuous variables the number of non-missing observations, mean, standard deviation, median, minimum and maximum will be presented.

Categorical data will be summarized using frequency and percentage. 95% confidence interval may be constructed around the percentage values for some variables. Some of the variables may also be summarized by country.

The educational materials will be considered to be effective if at least 80% of physicians will have responded correctly to at least 75% of the questions in the survey in which knowledge on the educational material is assessed.

This hypothesis is based on empirical numbers.

Evaluation of the success rate will be based on the percentage of correct answers to questions A2 to A5 in Section 4 ("Awareness and knowledge of risk minimisation measures") of the survey questionnaire.

Two analyses to evaluate the effectiveness of the risk minimization measures will be performed:

In the main analysis all questionnaires will be evaluated. In the subgroup analysis, only questionnaires of the physicians who answered "Yes" to question A7 ("Did you receive educational material regarding Intuniv[®]?") will be included. The subanalysis will allow to evaluate if awareness of the educational material may affect the number of correct answers.

More detailed information regarding the evaluation of the effectiveness is given in the survey SAP.

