4.6 Variables

The collected information includes:

- Physician related data (demographics, setting, prescriber's specialty)
- Drug utilization data: indication of use/diagnosis, patient characteristics (age, gender, comorbidities), data on patterns of drug use (dosing, first time user, repeat user, duration, discontinuation of ADHD therapy and switches), frequency of monitoring and weight, blood pressure, heart rate if information is available.

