8.2 OBJECTIVES

Primary objectives:

- To characterize patients who are prescribed Intuniv® with a specific focus on
 - o Indications other than ADHD
 - o Children less than 6 years of age
 - o Adults
 - O Patients who did not have any first-line stimulant treatment prior to their first prescription of Intuniv®
 - o Prescribed overdose of >7 mg/day, or of >4 mg/day for patients ≤12 years of age
- To describe prescribing patterns of Intuniv® among physicians

Secondary objective:

• To measure the effectiveness of the additional risk minimisation measure (educational materials for healthcare professionals) in order to assess compliance with the indication and with visits and measurements needed during the first year of treatment

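### Each physician reports 1 to 10 patients whatever the caseload, and no caseload is listed for collection, so the pooled off-label percentages may over-weight low-volume prescribers

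*Protocol*

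**What the plan says.** Section 8.2 of the protocol sets the target as patients: "To characterize patients who are prescribed Intuniv", with particular attention to five kinds of possible off-label use.

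The sample is drawn in two stages.

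- **Physicians.** Section 9.2 says "physicians will be randomly recruited using nationally representative external lists (OneKey lists". Section 9.5.1 adds "It is planned to annually recruit 15 to 20 prescribers of Intuniv[®] per country" and "Due to the low prescribing base, no quotas by physician types will be set". Selection in proportion to caseload is not described.
- **Patients within physician.** Section 9.2 says "One to 10 patients per physician may be reported, with the most recent patients being reported first". The number is not tied to caseload. The overall goal in section 9.5.1 is "Per country and year, the target is to collect data from 50 to 100 patients".

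For the analysis, section 9.7.3 says "Categorical data will be summarized using frequency and percentage". Section 9.7.1 gives results by country, without stratification by specialty. On the physician side, section 4.6 lists "Physician related data (demographics, setting, prescriber's specialty", and section 9.3 repeats those three items. Neither lists the number of Intuniv patients a physician has.

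**The concern.** Within a physician who has N patients in the selection window and reports n of them, a patient's chance of being reported is about n/N. A prescriber with 3 patients can report all of them. One with 40 can report at most 10, or 25%. If records are pooled and counted equally, each patient of the low-volume prescriber carries up to four times the weight of a patient of the high-volume prescriber.

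This matters only if off-label use differs between the two kinds of prescriber. That is plausible, because the sampling lists mix GPs with paediatricians, psychiatrists and neurologists. The percentages at stake are the primary results: non-ADHD indication, age under 6, adults, no prior stimulant, and overdose. A shift of this kind is separate from the width of the interval, and adding records under the same cap does not reduce it. The limitations in section 9.9 cover voluntary participation and web-survey bias but not this.

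**Working it through.** **The plan's own figure.** Section 9.5.2 uses n = p(1−p)z²/e² with p = 0.5 and 95% confidence.

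- e = 0.05: 0.25 × 1.96² / 0.05² = 384.1 (stated: 384).
- e = 0.10: 0.25 × 1.96² / 0.10² = 96.04, rounded up to 97 (stated: 97, taken as 100).

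Both reproduce. The formula treats the records as a simple random sample in which every patient has the same chance of inclusion.

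**Records per physician.** From section 9.5.1, 50 to 100 records come from 15 to 20 physicians. The average lies between 50/20 = 2.5 and 100/15 = 6.7.

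**Formulas.** Let physician i have N_i patients, report n_i = min(N_i, 10), and have off-label proportion p_i. Assume physicians within a country are equally likely to be included.

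- Pooled record percentage = Σ n_i p_i / Σ n_i
- Percentage among those physicians' patients = Σ N_i p_i / Σ N_i

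**Inputs that are assumed.** The protocol gives no caseloads and no off-label rates. The illustration takes 17 physicians, within the planned 15 to 20: 12 with 3 patients each and 5 with M patients each. Records number 12×3 + 5×10 = 86.

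| M | Off-label, low / high volume | Pooled records | All patients | Shift (points) |
|---|---|---|---|---|
| 40 | 30% / 5% | 13.3/86 = 15.5% | 20.8/236 = 8.8% | +6.7 |
| 20 | 30% / 5% | 13.3/86 = 15.5% | 15.8/136 = 11.6% | +3.9 |
| 15 | 30% / 5% | 13.3/86 = 15.5% | 14.55/111 = 13.1% | +2.4 |
| 40 | 5% / 30% | 16.8/86 = 19.5% | 61.8/236 = 26.2% | −6.7 |

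**A second set of assumptions.** Take 15 physicians with 3 patients and 5 with M, with off-label rates of 30% and 10%.

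- M = 8 or 10: no shift, because all patients are reported.
- M = 20: 19.5% pooled against 16.2%.
- M = 40: 19.5% against 13.7%. Low-volume physicians hold 45/245 = 18.4% of patients but supply 45/95 = 47.4% of records.
- Rates reversed: 20.5% against 23.8% (M = 20) and 26.3% (M = 40).
- Equal rates of 20%: no shift at any M.
- At most 5 records per physician in practice, M = 20: 22.9% against 16.2%. The shift can therefore arise below the formal cap of 10.

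**Cost of weighting.** In the first illustration with M = 40, 50 records have weight 4 and 36 have weight 1. The Kish effective sample size is (Σw)²/Σw² = 236²/836 = 66.6, so about 67 of 86.

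**The case against.** **The sentence in 9.7.3 is generic, and the SAP is not shown.** It does not say unweighted, and section 9.7.1 leaves table shells and variable definitions to the SAP. A SAP may well specify weights. This stands as far as the estimator goes. It does not dispose of the data item: section 9.3 is the protocol's list of what will be collected, and a weight cannot be built from a number nobody records. The questionnaire is a separate document and may already ask for it; that cannot be checked here.

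**The cap may rarely bind.** Section 9.5.2 expects very few patients, section 9.5.1 cites a low prescribing base, and the planned average is 2.5 to 6.7 records per physician. This is the strongest point, and it is why the concern is conditional. It is not complete, however. Reporting up to 10 is optional, at about 10 extra minutes per patient (section 9.4), and recruitment stops once the target is reached (section 9.6.1), so reported numbers can fall short of caseload below 10. The first survey also covers the time since launch, about 29 months in Belgium and the Netherlands and about 35 in Finland and Ireland by Table 2.

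**The scenarios are invented.** True. Five physicians with 40 patients each and a six-fold difference in rates have no support in the protocol. They show possible size only.

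**Stratifying by specialty would not cure this.** Correct. Specialty is not caseload, so the absence of that stratification is not part of the fault.

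**Little hangs on it.** The analysis is descriptive. The only threshold, 80% of physicians in section 9.7.3, is at physician level and unaffected.

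**Conclusion.** The point holds in conditional form. The number of records per physician is not tied to caseload, the stated summary is a plain percentage, and the listed variables do not include caseload. The pooled percentages may therefore misstate off-label use among patients prescribed Intuniv, but only if (a) some physicians have more patients than they report and (b) off-label use varies with caseload. The direction is unknown. With assumed high-volume caseloads of 15 to 40, the shift is about 2 to 7 points, against the planned precision of 10. It is nil if either condition fails.

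A reader might infer that the percentages definitely fail to estimate use among Intuniv patients. The protocol does not support that: it shows neither condition and expects low numbers. A reader might also infer that a weighted figure should replace the unweighted one as the basis for conclusions. That does not follow either. Reported patients are the most recently seen rather than a random draw, participation is voluntary, and weighting costs effective sample size. What can be said is that without caseload nobody will be able to tell whether the pooled percentages are affected. This is a cheap improvement to a descriptive study.

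**What to change.** 1. In section 9.3, add to the physician data: *number of patients prescribed Intuniv in the selection window*, unless the questionnaire already asks for it.
2. In section 9.7.3, report each primary off-label percentage weighted by N_i/n_i within country as a sensitivity result, beside the unweighted percentage.
3. State that the unweighted percentage describes reported records, and that a material difference between the two limits inference to patients prescribed Intuniv.

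The cost is one question per physician and one column per table. Caseload would be self-reported, and the weighted interval would be wider (about 67 effective records of 86 in the 40-patient illustration). Weighting does not correct for selecting the most recent patients or for voluntary participation, and the report should say so.
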